2.7.2.6 TSQM

The TSQM scale scores (Effectiveness, Convenience and Global satisfaction) will be summarized by visit. A summary of TSQM scale scores will be presented graphically over visits overall and by subpopulation.

2.7.2.7 PBI

The PBI global score will be summarized by visit. A summary of the PBI will be displayed graphically over time by subpopulation.

2.7.3 Handling of missing values/censoring/discontinuations

The last observation carried forward (LOCF) method will be applied to all secondary variables.

Any missing individual items will not be imputed. Handling of missing items within each questionnaire is described in the [Appendix 5.4](#).

For each questionnaire, where it is allowed to skip questions (DLQI, HAQ-DI, PBI, TSQM [REDACTED]), the percentage of missing items and will be presented over visits. In addition the percentage of scores/index values imputed with LOCF will be presented by visit.

2.8 Safety analyses

One of the secondary objectives is to assess the overall safety and tolerability of treatment with secukinumab 300 mg in 3 pre-defined subpopulations and in the overall study population.

All safety analyses will be performed on the Safety set, overall and by subpopulation.

2.8.1 Adverse events (AEs)

AE summaries will include all treatment emergent AEs (TAES), i.e. AEs starting after first dose study drug.

AEs will be summarized by number and percentage of subjects having at least one AE, having at least one AE in each primary system organ class (SOC) and for each preferred term (PT) using MedDRA coding. A subject with multiple occurrences of an AE will be counted only once in the respective AE category.

In AE summaries, the primary system organ class will be presented alphabetically and the preferred terms will be sorted within primary SOC in descending frequency. The sort order for the preferred term will be based on their overall frequency.

The following adverse event summaries will be produced; overview of AEs and deaths, AEs by SOC and PT, summarized by relationship to study, severity, leading to treatment discontinuation, leading to dose interruption/adjustment, requiring additional therapy and leading to fatal outcome. In addition, SAEs will be summarized by SOC and PT overall and for those leading to treatment discontinuation.

All AEs collected in the AE eCRF page will be listed along with the information collected on those AEs e.g. AE relationship to study drug, AE outcome etc. AEs with start date prior to first dose of study drug will be flagged in the listings. AEs for screen failures will be listed separately.

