A SAE is defined as event which:

- Is fatal or life-threatening.
- Results in persistent or significant disability/incapacity.
- Constitutes a congenital anomaly/birth defect.
- Requires inpatient hospitalization or prolongation of existing hospitalization, unless hospitalization is for:
 - Routine treatment or monitoring of the studied indication, not associated with any deterioration in condition.
 - Elective or pre-planned treatment for a pre-existing condition that is unrelated to the indication under study and has not worsened since signing the informed consent.
 - Treatment on an emergency outpatient basis for an event not fulfilling any of the definitions of a SAE given above and not resulting in hospital admission.
 - Social reasons and respite care in the absence of any deterioration in the patient's general condition.

Is medically significant, i.e. defined as an event that jeopardizes the patient or may require medical or surgical intervention to prevent one of the outcomes listed above. Examples include allergic bronchospasm (a serious problem with breathing) requiring treatment in an emergency room, serious blood dyscrasias (blood disorders) or seizures/convulsions that do not result in hospitalization. The development of drug dependence or drug abuse would also be examples of important medical events. All malignant neoplasms will be assessed as serious under "medically significant" if other seriousness criteria are not met.

Unlike routine safety assessments, SAEs are monitored continuously and have special reporting requirements; see [Section 7.2](#).

All AEs should be treated appropriately. Treatment may include one or more of the following: no action taken (i.e. further observation only); study drug temporarily interrupted; study drug(s) permanently discontinued; concomitant medication given; non-drug therapy given. The action taken to treat the AE should be recorded on the AE eCRF.

Once an AE is detected, it should be followed until its resolution or until it is judged to be permanent, and assessment should be made at each visit (or more frequently, if necessary) of any changes in severity, the suspected relationship to study drug, the interventions required to treat it, and the outcome.

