9.5.2 Safety variables

Analysis of safety data will be based on the Safety set.

Adverse events

The assessment of safety will be based primarily on the frequency of AEs and SAEs. SAEs suspected by the Investigators to be related to the prescribed medication will be summarized as appropriate.

The only AEs that will be counted will be treatment-emergent AEs (TEAEs). A TEAE is defined as any AE that develops after initiation of the study treatment or any event already present that worsens following exposure to the study treatment. This definition is not used by the Investigator, but rather is used in the analysis and reporting of clinical trial data. A patient with multiple AEs within a body system will only be counted once towards the total of this body system.

The incidence of AEs (new or worsened) will be summarized by primary SOC, preferred term, severity and relationship to study drug. In addition, the incidence of death, SAEs, and AEs leading to discontinuation will be summarized separately by primary SOC and preferred term.

All AEs will be displayed by group and patient.

Vital signs

All vital signs (including height and weight) will be summarized by prior psoriasis treatment group and visit and listed by group, patient and time. Analysis of the vital sign measurements using summary statistics for the change from Baseline for each post-Baseline visit will be performed.

Clinical laboratory evaluations

The summary of laboratory evaluations will be presented for the hematology, clinical chemistry, and fasting laboratory tests. Descriptive summary statistics for the change from Baseline to each visit will be presented. These descriptive summaries will be presented by laboratory test and prior psoriasis treatment group. Changes from Baseline will only be summarized for patients with both Baseline and post Baseline data.

Shift tables will be provided for all parameters to compare a patient's Baseline laboratory evaluation relative to the most extreme observed value during the treatment phase. For the shift tables, the normal laboratory ranges will be used to evaluate whether a particular laboratory test value was normal, low, or high for each visit value relative to whether or not the Baseline value was normal, low, or high. These summaries will be presented by laboratory test and treatment group. Shifts will be presented by visit as well as for most extreme values post-Baseline.

Physical examinations

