2.14 Interim analysis

An interim analysis describing the self-reported baseline characteristics and HR-QoL of patients prior to treatment will be performed for this study after LPFT.

The interim analysis will be based on the Safety set.

Patient screening phase disposition, demographics, baseline disease characteristics, baseline IGA mod 2011, PASI and PROs will be presented as described in [Section 2.3](#).

Other medical history and prior medications and non-drug therapies will not be part of the interim analysis.

3 Sample size calculation

The study aims to estimate primarily the effect of 16 weeks treatment with secukinumab 300 mg on the QoL of the overall study population as well as within the 3 pre-defined subpopulations. It is expected that 40% of the overall study population will fulfil the criteria

for the definition of subpopulation A; 40% will fulfil the criteria for subpopulation B; and 20% will fulfil the criteria for subpopulation C.

The DLQI 0/1 response rate in the overall population treated with secukinumab 300 mg s.c. is expected to be around 70% at Week 16; however, it may vary within those pre-defined subpopulations. A total of 323 patients are required to estimate the response rate of DLQI 0/1 with a precision (= 95% CI) of 5% if the true response rate is about 70% in the smallest subpopulation. To ensure that this precision is achieved in the 3 subpopulations (defined in Section 3.1), which consist of 20% to 40% of the overall study population, 1 615 patients in total should be recruited into this trial.

4 Change to protocol specified analyses

According to the protocol all data from physical examinations should be summarized and listed. As these data are only collected in the source data (see Section 6.5.1 of the protocol) this will not be analyzed.

5 Appendix

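### SAP 2.8.1 drops the worsening half of the protocol's treatment-emergent AE definition without declaring it, so AEs with a pre-dose start date that worsen on treatment are missing from the AE summaries

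*SAP*

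**What the plan says.** Protocol 9.5.2 limits AE counts to treatment-emergent events and gives the definition two limbs: "A TEAE is defined as any AE that develops after initiation of the study treatment or any event already present that worsens following exposure". The planned tables follow from it: "The incidence of AEs (new or worsened) will be summarized by primary SOC, preferred term, severity and relationship to study drug".

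SAP 2.8.1 has one limb, based on start date: "AE summaries will include all treatment emergent AEs (TAES), i.e. AEs starting after first dose study drug". The same section plans the overview and the tables by system organ class and preferred term, severity, relationship, treatment discontinuation, interruption or adjustment, additional therapy and fatal outcome, as well as the SAE tables. For AEs that began before dosing it provides only this: "AEs with start date prior to first dose of study drug will be flagged in the listings".

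SAP Section 4 has a single entry, which begins "According to the protocol all data from physical examinations should be summarized and listed" and explains why that will not be done. The AE definition is not mentioned there.

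**The concern.** SAP Section 2 says its methods rest on Section 9 of the protocol with added detail. A reader who finds only the physical examination entry in Section 4 will assume that the protocol's AE definition still governs the tables. It does not.

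Safety and tolerability is a secondary objective, both overall and in each of the three subpopulations. An event that was mild during screening and then led to discontinuation on secukinumab would count under the protocol but be absent from the discontinuation table under the SAP. The error runs in one direction, since removing a limb of the definition can only remove events. In the general AE tables a few missing events would hardly show. In the SAE and discontinuation tables, where counts are smaller, single events matter more.

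**Working it through.** No figure in the plan needs reproducing, because the point concerns a definition. The check is to apply both rules to each kind of event.

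**Inputs**

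- Protocol 6.1 and 7.1: AEs are recorded from informed consent, so AEs with a pre-dose onset will be in the database. SAP 2.8.1 expects them, since it flags them.
- Protocol Section 6: screening has flexible length, with a recommended limit of 4 weeks.
- Protocol 6.2.5: conditions present before consent go to the medical history page.
- Protocol 7.1: a condition present before study drug becomes an AE only if it worsens once drug has started.
- Protocol 7.1, on an AE already detected: "assessment should be made at each visit (or more frequently, if necessary) of any changes in severity". It does not say whether worsening updates the existing record or opens a new one.
- Protocol 7.2: progression of an SAE is reported as follow-up to the original episode. This rule is about SAE reporting.
- Protocol 7.1, AE page contents: severity grade, relationship, start and end dates, seriousness, action taken with study drug, concomitant therapy and outcome. No dated change-of-severity field is listed.

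**Both rules applied**

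| Event | Protocol 9.5.2 | SAP 2.8.1 summaries |
|---|---|---|
| AE starting after first dose | Counted | Counted |
| AE starting between consent and first dose, worsens on drug, kept as one record | Counted | Not counted; flagged listing only |
| Same, but worsening opens a new record dated after first dose | Counted | Counted |
| Medical-history condition that worsens on drug, AE dated at worsening | Counted | Counted |
| Same, AE dated at original onset | Counted | Not counted; flagged listing only |

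The two rules disagree in rows 2 and 5. In both, the recorded start date precedes the first dose. Whether rows 2 and 5 or rows 3 and 4 describe actual recording practice depends on a dating convention that neither document gives. For SAEs, the follow-up rule in Protocol 7.2 points towards row 2.

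**Consistency within the SAP.** SAP 2.8.3 summarizes both CTCAE laboratory grades and liver function abnormalities as newly occurring or worsening. Worsening is therefore kept for laboratory safety and lost only for AEs.

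**The case against.** The best counter-argument is that the worsening limb mainly concerns long-standing conditions. Under Protocol 7.1 these become AEs only when they worsen on drug, so a post-dose start date is the natural reading and the SAP rule would include them. The clearly exposed group is then AEs with onset in a screening period of about 4 weeks. All AEs are listed, with pre-dose onset flagged. A patient with any other post-dose AE still counts in the overall incidence. The study is single-arm and descriptive. All of this stands, and it limits the reach of the point. It does not remove the contradiction between the two definitions or the silence of Section 4.

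Three stronger readings are tempting and not supported:

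- *Every pre-existing event that worsens disappears from every AE table.* Events dated at worsening are included, and the documents do not fix the dating.
- *Deaths are lost.* The fatal-outcome AE table falls under the start-date rule, but SAP 2.8.2 separately summarizes the primary reason for death and lists all deaths, with no treatment-emergent restriction stated.
- *The number of patients affected can be estimated.* Assuming that 5–10% of 1,615 patients have a screening AE and 10–20% of those worsen gives 1,615 × 0.05 × 0.10 ≈ 8 to 1,615 × 0.10 × 0.20 ≈ 32. Both rates are guesses with no basis in the documents, and the product also assumes that every such AE keeps its pre-dose start date. It should not be cited as a finding.

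**Conclusion.** The concern holds in limited form. The SAP's definition is narrower than the protocol's, and the change is undeclared. AEs recorded with a pre-dose start date that worsen on treatment are left out of the AE, SAE and discontinuation summaries. The direction is certain: incidence can only fall relative to the protocol's definition. The size is unknown, because it depends on how many AEs start between consent and first dose, how many of those worsen, and whether worsening is entered on the original record. The documents give none of these. The point should be corrected before the tables are produced, but it does not call the study's safety conclusions into question.

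**What to change.** In SAP 2.8.1, restore the protocol definition: AEs starting after the first dose, or already present and worsening after it. Apply it to all AE summaries, including SAEs, discontinuation, interruption and fatal outcome.

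State how worsening is identified from what is collected. Two routes are available:

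- a new AE record dated at worsening; or
- for a record with a pre-dose start, a post-dose change to serious, or an action or outcome of drug discontinuation, interruption or death.

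State also which start date applies when a medical-history condition becomes an AE on worsening.

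If the start-date rule is kept, declare and justify it in SAP Section 4, and add a table of AEs with pre-dose onset that worsened on treatment.

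The cost is SAP wording and a small derivation change. There is one limitation to acknowledge: if the AE page holds a single severity grade per record, worsening in severity alone may not be fully identifiable, and the SAP should say so.

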3.6 Risks and benefits

Secukinumab has shown confirmed efficacy in psoriasis and preliminary efficacy in several inflammatory diseases, e.g. rheumatoid arthritis, ankylosing spondylitis, PsA: up to 12 000 patients have been enrolled in studies with secukinumab with over 9 600 having received active drug at doses ranging from single and/or multiple doses of 0.1 mg/kg to 30 mg/kg i.v. and 25 mg to 300 mg s.c. An extensive Phase 2/3 program (conducted in 4 546 patients, 3 430 of those treated with secukinumab) demonstrated secukinumab to be very effective in treating plaque psoriasis, with 300 mg being the dose that delivered the highest benefit to patients with respect to achievement of almost clear to clear skin, improved QoL, speed of onset of action, and sustainability of symptom relief. From a safety perspective, secukinumab was overall well tolerated.

Secukinumab has the potential to increase the risk of infections. In clinical studies, infections have been observed in patients receiving secukinumab. Most of these were mild or moderate

upper respiratory tract infections such as nasopharyngitis and did not require treatment discontinuation. Related to the mechanism of action of secukinumab, non-serious mucocutaneous *Candida* infections were more frequently reported for secukinumab than placebo in the psoriasis clinical studies (3.55 per 100 patient years for secukinumab 300 mg versus 1.00 per 100 patient years for placebo). Caution should be exercised when considering the use of secukinumab in patients with a chronic infection or a history of recurrent infection, and exclusion criteria are applied in this study to minimize the risk (Section 4.2). Patients will be instructed to seek medical advice if signs or symptoms suggestive of an infection occur.

If a patient develops a serious infection, the patient will be closely monitored and secukinumab should not be administered until the infection resolves. No increased susceptibility to tuberculosis was reported from clinical studies. However, secukinumab should not be given to patients with active tuberculosis. Anti-tuberculosis therapy should be considered prior to initiation of secukinumab in patients with latent tuberculosis. Exclusion criteria are applied in this study to minimize the risk (Section 4.2) and additional guidance is provided in Section 6.2.7.

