Caution should be exercised when treating with secukinumab patients with Crohn's disease as exacerbations of Crohn's disease, in some cases serious, were observed in clinical studies in both secukinumab and placebo groups. Patients who are treated with secukinumab and have Crohn's disease will be eligible but will be followed closely.

If an anaphylactic or other serious allergic reaction occurs, administration of secukinumab should be discontinued immediately and appropriate therapy initiated.

The removable needle cap of the PFS contains a derivative of natural rubber latex. No natural rubber latex has to date been detected in the removable needle cap. Nevertheless, the use of secukinumab PFS in latex-sensitive individuals has not been studied and there is therefore a potential risk of hypersensitivity reactions, which cannot be completely ruled out. Exclusion criteria are applied in this study to minimize the risk (Section 4.2).

Live vaccines should not be given concurrently with secukinumab. Patients receiving secukinumab may receive concurrent inactivated or non-live vaccinations. In a study, after *meningococcal* and inactivated influenza vaccinations, a similar proportion of healthy volunteers treated with 150 mg of secukinumab and those treated with placebo were able to achieve an adequate immune response of at least a 4-fold increase in antibody titers to *meningococcal* and influenza vaccines. The data suggest that secukinumab does not suppress the humoral immune response to the *meningococcal* or influenza vaccines. Exclusion criteria are applied in this study to minimize the risk (Section 4.2).

Most of the experience to date has been with secukinumab s.c. doses up to 300 mg and i.v. doses up to 10 mg/kg; there are limited data at this time for higher doses. No cases of overdose have been reported for secukinumab. Single doses of secukinumab up to 30 mg/kg (i.e. approximately 2 000 to 3 000 mg) have been administered i.v. in clinical studies in other autoimmune indications, and doses up to 3×10 mg/kg i.v. have been administered in psoriasis studies without acute dose-limiting toxicity.

Adverse events (AEs)/serious adverse events (SAEs) occurring during clinical trials with secukinumab should be managed based on the best clinical judgment of the Investigator in the context of the underlying disease and treated as clinically warranted.

Novartis standard processes aligned with international guidelines apply for the reporting of safety events.

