6.5 Safety

From Day 1 (Baseline Visit), all blood draws and safety assessments must be performed as indicated in [Table 6-1](#) prior to study drug administration. Appropriate safety assessments (e.g. evaluation of AEs and SAEs) should be repeated after the dose of study drug is administered.

- Evaluation of all AEs and SAEs including injection site hypersensitivity reactions, vital signs, laboratory assessments and occurrence of infections (see [Section 7](#)).
- Physical examination.
- Vital signs.
- Height and weight.
- Laboratory evaluations (hematology, clinical chemistry, urine dipstick).
- Fasting laboratory tests (glucose, lipid profile, HbA1c and hsCRP).
- Pregnancy and assessments of fertility.

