2.8.1.1 AEs of special interest / grouping of AEs

Not applicable.

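### Adverse events are planned only as crude percentages by SOC and preferred term; with unequal follow-up by design, grouped terms and exposure-adjusted rates would be a cheap improvement

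*SAP*

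**What the plan says.** SAP 2.8.1 sets the summary measure for treatment-emergent events: "AEs will be summarized by number and percentage of subjects having at least one AE", then the same by primary SOC and by preferred term. There are further cuts by relationship, severity, discontinuation, interruption or adjustment, additional therapy and fatal outcome, and separate SAE tables. The counting rule is "A subject with multiple occurrences of an AE will be counted only once in the respective AE category". The next section, headed "AEs of special interest / grouping of AEs", is marked as not applicable. SAP 2.8 makes all safety analyses overall and by subpopulation, in line with the secondary safety objective.

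The protocol sets the same kind of measure. Section 9.5.2 reads "The assessment of safety will be based primarily on the frequency of AEs and SAEs", and it counts a patient once per body system.

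Protocol 3.6 describes the risks. It says "Secukinumab has the potential to increase the risk of infections", gives non-serious mucocutaneous Candida infections as "3.55 per 100 patient years for secukinumab 300 mg versus 1.00 per 100 patient years for placebo", notes exacerbations of Crohn's disease, and has an instruction that begins "If an anaphylactic or other serious allergic reaction occurs". Protocol 6.5 lists the evaluation of AEs and SAEs, "including injection site hypersensitivity reactions, vital signs, laboratory assessments and occurrence of infections".

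On follow-up, protocol 3.1 asks that stopping be considered in patients with no response up to Week 16. SAP 2.1.1 confirms that a patient may complete treatment phase 1 and not enter phase 2.

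**The concern.** There are two separate gaps.

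The first is the numerator. Where a named risk is coded to more than one preferred term, the rows cannot be added to give the number of patients affected, because one patient may appear in several rows. Without a grouping, no planned row gives that number for Candida infection, hypersensitivity, injection-site reactions or inflammatory bowel disease.

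The second is the denominator. A percentage of all treated patients takes no account of time observed. If some patients are watched for 16 weeks and others for 52, the percentage falls as the share of early stoppers rises, with no change in the underlying rate. Subpopulations A, B and C are defined by prior treatment failure or intolerance, so early stopping for non-response could plausibly differ between them. If it did, their AE percentages would differ for that reason alone. A percentage also cannot be placed directly beside a figure per 100 patient-years, the scale on which the protocol quotes its only numerical AE risk.

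**Working it through.** **The quoted rate.** The 3.55 per 100 patient-years cannot be reproduced, because the documents give neither the cases nor the patient-years behind it. It is used here only as an assumed true rate.

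**Number of patients.** Protocol 9.7 and SAP 3 give 323 for the smallest subpopulation and 1615 in total. Both reproduce: 1.96² × 0.7 × 0.3 / 0.05² = 322.7, so 323; and 323 / 0.20 = 1615. Protocol 5.2 gives 646 each for A and B.

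**Assumptions.** A share s stops at Week 16 and is observed no further; the rest are observed for 52 weeks. The hazard is constant at 0.0355 per year, and a year is 52.18 weeks. The documents give no dropout figure, so s = 5%, 10% and 20% are illustrative.

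**Formulas.**
- Patient-years = 1615 × [(1 − s) × 52 + s × 16] / 52.18
- Expected patients with an event ≈ 0.0355 × patient-years
- Crude % = (1 − s) × [1 − exp(−0.0355 × 52/52.18)] + s × [1 − exp(−0.0355 × 16/52.18)] = (1 − s) × 3.476% + s × 1.083%

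**Results.**

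| s | Patient-years | Expected events | Exact Poisson 95% CI, per 100 patient-years | Crude % |
|---|---|---|---|---|
| 5% | 1554 | 55 | 2.67 to 4.61 | 3.36 |
| 10% | 1498 | 53 | 2.65 to 4.63 | 3.24 |
| 20% | 1387 | 49 | 2.61 to 4.67 | 3.00 |

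The same true rate therefore prints as 3.36% or 3.00%, a difference of 0.36 percentage points due only to stopping. As wider bounds, with 52 weeks taken as one year, the crude figure is 3.49% with no early stopping and 2.53% if 40% stop at Week 16. Relative to 3.55 these are 2% and 29% lower.

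**Size in the smallest subpopulation.** In C, 323 × 3.36% = 10.8 and 323 × 3.00% = 9.7 expected patients, a difference of about one. The exact 95% CI for 10 of 323 is 1.5% to 5.6%, far wider than that difference.

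**What a rate would show.** With a full year of follow-up at the assumed rate:
- A or B: 23 cases in 646 patient-years, 3.56 (95% CI 2.26 to 5.34) per 100 patient-years.
- C: 11 cases in 323 patient-years, 3.41 (1.70 to 6.09).

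The overall estimate is informative; the one for C is wide.

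**Are the ingredients there?** SAP 5.1.2 requires complete AE dates, SAP 2.8.1 lists every AE, and SAP 2.4.1 summarizes exposure in days. There is one hole in the denominator. The exposure rule in SAP 2.4.1 covers patients who discontinue in phase 1, complete the study or discontinue in phase 2. It does not name those who complete phase 1 without entering phase 2, the group that makes follow-up unequal. The date-of-last-contact rule in SAP 2.1.1 does cover them.

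**The case against.** The strongest reply is that nothing promised is missing. The SAP follows protocol 9.5.2, the 3.55 is background in a risk-benefit section, and no objective asks for a check against it. Protocol 3.3 expects no new safety signals, and protocol 8.4 records that substantial safety data already exist. All of this stands: the point is an omission, and the plan does not contradict itself.

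Three stronger readings are tempting, and the documents do not support them.
- A reader might infer that the trial is unable to state these rates. It is able to. Dates, listings and exposure are collected, and n × mean exposure from the planned tables already gives approximate patient-years.
- A reader might infer that none of the named risks gets a patient-level count. Infections do, because each patient is counted once in the SOC row, and any risk coded to a single preferred term does too. How far the other risks are split over terms depends on coding that the documents do not show.
- A reader might infer that AE comparisons between A, B and C are biased. That needs stopping to differ between them, which is undocumented. Disposition by phase and subpopulation (SAP 2.3.1) and the exposure thresholds (SAP 2.4.1) would reveal an imbalance.

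A rate also has limits. It removes the effect of follow-up length only if the hazard is roughly constant. For events concentrated in the first weeks, stopping at Week 16 hardly changes the crude percentage, and the rate would be the measure that moves. That is a reason to report both.

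**Conclusion.** The point holds as a modest gap in the planned outputs. As written, the AE tables give crude percentages by SOC and preferred term, with no grouped terms and no exposure-adjusted rate, while follow-up differs by design between 16 and 52 weeks. The percentages in A, B and C therefore depend partly on how many patients stop at Week 16, and cannot be set directly against 3.55 per 100 patient-years. Under a constant hazard and an assumed 5% to 20% stopping, the Candida figure moves from about 3.4% to 3.0%, which is well inside sampling error in C. The case for the change is that it is cheap, uses data already collected and serves the secondary safety objective by subpopulation. Naming the groups in advance in an open-label study also avoids choosing terms after the listings have been seen. One limit: SAP 2.13 is not visible. SAP 2.11 describes it only as other exploratory analysis, so related content there cannot be excluded.

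**What to change.** 1. In SAP 2.8.1.1, replace the present entry with medically signed-off MedDRA groupings for the protocol 3.6 and 6.5 risks that have no row of their own: non-serious mucocutaneous Candida infection, hypersensitivity, injection-site reactions and inflammatory bowel disease. Count each patient once per group.
2. For these groups, the infections SOC, all AEs and SAEs, report patients with a first event per 100 patient-years with 95% CI, overall and by subpopulation, beside the crude percentages.
3. Define time at risk as first dose to first event or end of observation, whichever is earlier. The date of last contact in SAP 2.1.1 could serve as end of observation.
4. Extend the exposure rule in SAP 2.4.1 to patients who complete phase 1 without entering phase 2.
5. State that any comparison with 3.55 is only indicative. The protocol does not say whether that figure counts first or all events, and it covers only non-serious mucocutaneous Candida infections.

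The cost is SAP text, a term list for medical sign-off and one or two extra tables. No new data are needed.
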